transvaginal ultrasound, and endometrial biopsy (only if required). When Week 52/Baseline procedures in the OLE study have been completed, the investigator will assess patient eligibility for participation in this study. The eligibility assessment will be based on data available at the Week 52/Baseline visit. No study procedures will be performed until the consent form is signed. Patients will receive the last dose of study drug in the OLE study on the day of the Week 52/Baseline visit (per the OLE protocol) and will be dispensed study drug for this Randomized Withdrawal study in the clinic after the patient is determined to be eligible for this study and has provided informed consent to participate. The first dose of study drug for the Randomized Withdrawal study will be self-administered the next morning following the Week 52/Baseline visit. Dosing will be confirmed by telephone.

Post-baseline Procedures: All post-baseline procedures are provided in the Schedule of Activities (Table 1-1).

Patients will be asked to provide feminine products for alkaline hematin analysis at each visit until the analysis confirms the return of heavy menstrual bleeding (defined as menstrual blood loss of ≥ 80 mL). The patients will then be offered retreatment with open-label relugolix with E2/NETA (latter also referred to as "add-back" in context of hormonal "add-back") with the onset of the next menses. They will resume collection of feminine products for alkaline hematin analysis until two consecutive analyses confirm resolution of heavy menstrual bleeding (menstrual blood loss of < 80 mL). Patients who experience a return of heavy menstrual bleeding (or terminate early because they have a return of heavy menstrual bleeding) but decline retreatment with open-label study drug will complete an Early Termination visit and a 30-day Safety Follow-up visit.

At the Week 104/Early Termination visit, all other patients will have an assessment of bone mineral density via dual-energy x-ray absorptiometry (DXA). Patients will complete the bleeding diary daily including compliance with study drug, vaginal bleeding, and use of feminine products.

The pharmacodynamic effect of withdrawal from relugolix with E2/NETA will be characterized by measuring the pre-dose concentration of estradiol at Week 56.

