4.3.7. Visit Windows

Visit windows, which will be used to associate assessments with a scheduled visit, will be used only for summarizing data by visit. The windows for scheduled assessments are shown in

Table 2 (for monthly assessment, SF-36v2, PGA, WPAI-UF), **Table 3** (for BMD), **Table 4** (for UFS-QoL), and **Table 5** (for clinical laboratory tests and vital signs), respectively. For both efficacy and safety assessments, the study day will be used to determine the associated visit window.

The data collected in the paper diary related to bleeding and use of FPs will be assigned to visit windows as specified in **Table 6** and will be used to calculate the feminine product return rate (FPRR) as specified in Section 7.3.2.5.

If the results from more than one assessment are within a given visit window, the non-missing result from the assessment closest to the target date will be used except for FP collection, which is specified in Section 7.3.2.4. If two assessments are equally close to the target day, the earlier assessment will be used. For summaries of shift from Baseline in safety parameters, all values will be considered for these analyses.

Table 2: Visit Windows for Monthly Assessments

Visit (Long label)	Visit (Short label)	Start Day	Target Day	End Day
Week 56 (4 weeks after randomization) ^a	Week 56	1	29	43
Week 60 (8 weeks after randomization)	Week 60	44	57	71
Week 64 (12 weeks after randomization)	Week 64	72	85	99
Week 68 (16 weeks after randomization)	Week 68	100	113	127
Week 72 (20 weeks after randomization)	Week 72	128	141	155
Week 76 (24 weeks after randomization)	Week 76	156	169	183
Week 80 (28 weeks after randomization)	Week 80	184	197	211
Week 84 (32 weeks after randomization)	Week 84	212	225	239
Week 88 (36 weeks after randomization)	Week 88	240	253	267
Week 92 (40 weeks after randomization)	Week 92	268	281	295
Week 96 (44 weeks after randomization)	Week 96	296	309	323
Week 100 (48 weeks after randomization)	Week 100	324	337	351
Week 104 (52 weeks after randomization)	Week 104	352	365	Date of last dose + 14 days ^b

^a Start day of Week 56 for study day 1 includes only post-Baseline assessments that occurred after the first dose.

^b For SF-36v2, PGA, WPAI-UF, 14 days after date of last dose is used as the end day of Week 104.

Table 3: Visit Windows for Bone Mineral Density Assessments

Visit (Long label)	Visit (Short label)	Start Day	Target Day	End Day
Week 104 (52 weeks after randomization)	Week 104	281	365	449

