Assessments will be excluded from analysis if they occur on or after the date of initiation of another investigational agent or hormonal therapy affecting the hypothalamic-pituitary-gonadal axis or surgical intervention for uterine fibroids. Assessments after date of last dose of study drug + 60 days will also be excluded from analysis.

Table 4: Visit Windows for UFS-QoL Assessments

Visit (Long label)	Visit (Short label)	Start Day	Target Day	End Day
Week 64 (12 weeks after randomization)	Week 64	64	85	106
Week 76 (24 weeks after randomization)	Week 76	148	169	196
Week 88 (36 weeks after randomization)	Week 88	197	253	308
Week 100 (48 weeks after randomization)	Week 100	309	337	351
Week 104 (52 weeks after randomization)	Week 104	352	365	421

Abbreviations: UFS-QoL = Uterine Fibroid Symptom and Health-Related Quality of Life.

Table 5: Visit Windows for Clinical Laboratory Tests and Vital Signs

Visit (Long label)	Visit (Short label)	Start Day	Target Day	End Day
Week 64 (12 weeks after randomization) ^a	Week 64	64	85	106
Week 76 (24 weeks after randomization)	Week 76	148	169	196
Week 104 (52 weeks after randomization)	Week 104	309	365	Date of last dose + 6 days
Safety Follow-Up ^b	Safety Follow-Up	Date of last dose + 7 days	Date of last dose + 30 days	Date of last dose + 60 days

^a This visit is only for clinical laboratory tests.

^b The safety follow-up visit window will be restricted to assessments prior to the date of initiation of another investigational agent or hormonal therapy affecting the hypothalamic-pituitary-gonadal axis or surgical intervention for uterine fibroids.

Table 6: Time Window for Feminine Product Collection

Visit (Long label)	Visit (Short label)	Feminine Product Collection Visit Date ^{a,b}	Time Window ^a
Week 56 (4 weeks after randomization) ^a	Week 56	X ₁	(Date of Study Day 1) – < X ₁
Week 60 (8 weeks after randomization)	Week 60	X ₂	(X ₁ +1) – ≤ X ₂
Week 64 (12 weeks after randomization)	Week 64	X ₃	(X ₂ +1) – ≤ X ₃
Week 68 (16 weeks after randomization)	Week 68	X ₄	(X ₃ +1) – ≤ X ₄
Week 72 (20 weeks after randomization)	Week 72	X ₅	(X ₄ +1) – ≤ X ₅
Week 76 (24 weeks after randomization)	Week 76	X ₆	(X ₅ +1) – ≤ X ₆
Week 80 (28 weeks after randomization)	Week 80	X ₇	(X ₆ +1) – ≤ X ₇
Week 84 (32 weeks after randomization)	Week 84	X ₈	(X ₇ +1) – ≤ X ₈
Week 88 (36 weeks after randomization)	Week 88	X ₉	(X ₈ +1) – ≤ X ₉
Week 92 (40 weeks after randomization)	Week 92	X ₁₀	(X ₉ +1) – ≤ X ₁₀

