4.4.1. By-Visit Endpoints

By-visit endpoints will be analyzed using observed data, unless otherwise specified. For observed data analyses, missing data will not be imputed and only the observed records will be included.

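### Gaps in the UFS-QoL and laboratory visit windows drop some Early Termination values from the by-visit summaries; an end-of-randomized-treatment row would recover them

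*SAP*

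**What the plan says.** SAP Section 4.3.7 assigns assessments to visits by study day: "For both efficacy and safety assessments, the study day will be used to determine the associated visit window". It limits the use of the windows: "Visit windows, which will be used to associate assessments with a scheduled visit, will be used only for summarizing data by visit". Where two results share a window, the one closest to the target day is kept.

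The UFS-QoL windows stand in "Table 4: Visit Windows for UFS-QoL Assessments", which opens with "Week 64 (12 weeks after randomization) Week 64 64 85 106", that is, start Day 64, target Day 85, end Day 106. The next row is "Week 76 (24 weeks after randomization) Week 76 148 169 196". Week 88 then takes Days 197–308, Week 100 Days 309–351 and Week 104 Days 352–421. Table 5 (laboratory tests and vital signs) has the same Week 64 and Week 76 windows, with Week 64 for laboratory tests only. Its Week 104 window then runs from Day 309 to six days after last dose, followed by a Safety Follow-Up window.

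SAP Section 4.4.1 adds: "By-visit endpoints will be analyzed using observed data, unless otherwise specified". Missing values are not imputed.

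Protocol Section 6.3 requires an Early Termination visit, with the Week 104 procedures, of everyone who withdraws before Week 104. Table 1-1 shows that these procedures include UFS-QoL and clinical laboratory tests. Protocol Section 4.1 states that women whose heavy bleeding returns but who "decline retreatment with open-label study drug will complete an Early Termination visit and a 30-day Safety Follow-up visit".

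**The concern.** An Early Termination visit is not tied to the UFS-QoL or laboratory schedule, so it can land on a day that belongs to no window. Such a value has no by-visit row, and the SAP names no end-of-treatment version for UFS-QoL or for mean hemoglobin change. It does define one for amenorrhea (Section 7.4.1.3.2) and for BMD (Section 9.3.3.1).

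These are the last values of women who are leaving, some of them because heavy bleeding has come back and they do not want open-label drug. At stake is whether the by-visit UFS-QoL and hemoglobin summaries for the randomized period describe everyone who supplied data, or leave out some values for a reason linked to outcome.

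**Working it through.** **Inputs.** Window limits and targets: SAP Tables 2, 4 and 5. Visit tolerances: Protocol Table 1-1. Dropout of 20% and 360 patients: SAP Section 2.2.

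**Step 1: reproduce the targets.** Target day = 7 × weeks since randomization + 1. Weeks 12, 24, 36, 48 and 52 give Days 85, 169, 253, 337 and 365, which match the tables.

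**Step 2: days in no window, out of Days 1–365.**

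| Table | Uncovered days | Total |
|---|---|---|
| 2 (SF-36, PGA, WPAI-UF) | none | 0 |
| 4 (UFS-QoL) | 1–63 (63), 107–147 (41) | 63 + 41 = 104 (28.5%) |
| 5, laboratory tests | 1–63 (63), 107–147 (41), 197–308 (112) | 63 + 41 + 112 = 216 (59.2%) |
| 5, vital signs | 1–147 (147), 197–308 (112) | 147 + 112 = 259 (71.0%) |

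**Step 3: days nearer another target (Table 4).** The midpoints are (85 + 169)/2 = 127, (169 + 253)/2 = 211, (253 + 337)/2 = 295 and (337 + 365)/2 = 351. The Week 88 window of 197–308 therefore takes Days 197–210 (14 days, nearer Week 76) and Days 296–308 (13 days, nearer Week 100), 27 days in all. Table 2 has no such days.

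**Step 4: scheduled visits.** With ±7 days (+10 at Week 104), UFS-QoL visits fall on Days 78–92, 162–176, 246–260, 330–344 and 365–375. All lie inside Table 4. Scheduled laboratory visits (Weeks 64, 76 and 104) lie inside Table 5. Only off-schedule values are exposed.

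**Step 5: exits at the nominal four-weekly visits.** An exit UFS-QoL score has no window at Weeks 56, 60, 68 and 72. It has one at Week 64 and from Week 76 on. An exit laboratory value has no window at Weeks 56, 60, 68, 72, 80, 84, 88 and 92, and has one at Weeks 64, 76, 96 and 100. For example, a woman leaving on Day 120 completes all four questionnaires. Table 2 places SF-36, PGA and WPAI-UF at Week 68 (Days 100–127), while Table 4 places her UFS-QoL nowhere.

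**Step 6: which outputs lose the value.**
- *UFS-QoL* (Section 7.4.2.11): the summaries are by visit, with responder and cumulative-distribution displays at Weeks 76 and 104. A gap-day score enters none of them.
- *Hemoglobin* (Sections 7.4.2.6 and 7.4.2.7): a gap-day value under Table 5 is absent from the by-visit change and anemia proportions. It remains in the shift tables, because Section 4.3.7 uses all values there. It also remains in the Appendix 2 thresholds, which Section 9.2 applies at any time and to the last on-treatment result.

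**Step 7: illustration of size.** The documents give no exit times, so these are assumptions. Take 20% × 360 = 72 dropouts, each with an Early Termination record.
- Exits uniform over 365 days: 72 × 104/365 = 20.5 UFS-QoL scores and 72 × 216/365 = 42.6 laboratory values on gap days.
- Exits exponential with 40% remaining at Day 169: h = −ln(0.4)/169 = 0.00542 per day. The share of exits before Day 365 that fall on gap days is 47% for UFS-QoL and 65% for laboratory tests, or 72 × 0.47 ≈ 34 and 72 × 0.65 ≈ 47.

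**The case against.** The case on the other side is substantial, and most of it stands.

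- **Hemoglobin is not lost altogether.** The any-time, last-on-treatment and shift outputs keep it in categorical form. It is also drawn with each feminine product return (Protocol Table 1-1 footnote). The SAP does not say whether that sample follows the monthly windows of Table 2, which have no gap, or Table 5. If Table 2 governs, that sample has no gap.
- **Coverage is better than the totals suggest.** UFS-QoL has no gap after Day 147. Laboratory values taken seven or more days after last dose go to Safety Follow-Up. That helps little, however, because the last dose is taken in clinic at the Early Termination visit.
- **Most relapsers need not leave.** Retreatment is offered, and only women who decline it exit this way; the documents do not say how many. For those who accept, Section 7.4.2.11 excludes later UFS-QoL scores from the randomized-period summary by explicit rule, not through the windows.
- **Early UFS-QoL scores are hard to read.** The questionnaire asks about the previous three months, so a score before Day 64 partly describes time before randomization. That may be a reason not to call it Week 64, though the SAP does not say so. It is not a reason to leave it out of every summary.

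A reader might infer that the gaps make the withdrawal arm look better, or that they undermine a missing-at-random model. The documents do not support either inference. They give no exit times by arm, and the recall period leaves the direction open. Section 7.1.2 excludes mixed models from the randomized period, and Section 7.4.2.6 makes cumulative-period hemoglobin descriptive. Section 7.1.2 does allow a model for UFS-QoL in the cumulative period, and a gap-day score would be missing from it, but nothing in the documents shows a resulting bias.

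**Conclusion.** The point holds in a limited form. Table 4 leaves 104 of 365 days uncovered and places 27 days under a visit that is not the nearest; Table 5 leaves 216 days uncovered for laboratory tests. Early Termination UFS-QoL scores on gap days enter no planned summary. Early Termination hemoglobin values on gap days, if Table 5 applies, miss the by-visit change and anemia summaries only.

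The loss can be informative, because women who relapse and decline retreatment exit through this visit. Its size and direction cannot be derived from the documents. The ranges of about 21 to 34 UFS-QoL scores and 43 to 47 laboratory values rest on assumed exit timing and on an Early Termination record for every dropout; for hemoglobin they also assume that Table 5 governs. It would be wrong to read the point as saying that all Early Termination values are lost.

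These are other secondary and safety summaries outside the testing sequence, so the primary and key secondary tests are unaffected. Severity is minor: a cheap improvement.

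**What to change.** 1. For UFS-QoL scores, hemoglobin change, other laboratory tests and vital signs, add an end-of-randomized-treatment row by treatment group. Define it as the last post-baseline value on randomized drug, including the Early Termination visit and before any retreatment. This follows the end-of-treatment approach already used for amenorrhea and BMD.
2. State whether Table 2 or Table 5 windows the hemoglobin sample drawn with each feminine product return.
3. Optionally, set the Table 4 boundaries at the midpoints 127, 211, 295 and 351. This corrects the 27 misassigned days but does not recover most exit scores, because the closest-to-target rule keeps one value per window. Suppose the Week 64 window were also opened at Day 43 and the woman had attended on schedule. Only Days 43–63 and 128–147 would be recovered, 21 + 20 = 41 of 104 gap days; an exit score on Days 107–127 would still lose to her Day 85 score. A Day 200 exit score, now kept as Week 88, would move to Week 76 and lose to her Day 169 score. The midpoints therefore should not replace the row in item 1.

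The cost is one extra row per output and one clarifying sentence. The row pools values taken at different times since randomization, and early UFS-QoL scores in it partly reflect the period before randomization. A footnote should say both.

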4.4. General Rules for Missing Data

Handling of missing data for the primary efficacy analysis is described in Section 7.3.3.

4.4.1. By-Visit Endpoints

By-visit endpoints will be analyzed using observed data, unless otherwise specified. For observed data analyses, missing data will not be imputed and only the observed records will be included.

4.4.2. Adverse Events and Concomitant Medications

The following imputation rules for the safety analyses will be used to address the issues with partial dates. The imputed dates will be used to determine the treatment-emergent period. For adverse events with a partial date, available date parts (year, month, and day) of the partial date will be compared with the corresponding date components of the start date and end dates of the treatment-emergent period to determine if the event is treatment emergent. When in doubt, the adverse event will be considered treatment emergent by default. If the adverse events were recorded in pivotal or LTE studies, the rules used to impute the partial dates in corresponding study will be used.

The following rules will be applied to impute partial dates for adverse events when they were newly recorded in the randomized withdrawal study:

- If start date of an adverse event is partially missing, impute as follows:
 - If both Month and Day are missing and Year = Year of treatment start date, then set to treatment start date, as long as adverse event end date is not prior to treatment start date;
 - If both Month and Day are missing and Year \neq Year of treatment start date, then set to January 1;
 - If Day is missing and Month and Year = Month and Year of treatment start date, then set to treatment start date, as long as adverse event end date is not prior to treatment start date;
 - If Day is missing and Month and Year \neq Month and Year of treatment start date, then set to first of the month;
 - If start date is completely missing, set to treatment start date, as long as adverse event end date is not prior to treatment start date.
- If end date of an adverse event is partially missing, impute as follows:
 - If both Month and Day are missing, then set to December 31;
 - If only Day is missing, then set to last day of the month;
 - If end date is completely missing, do not impute.

When the start date or end date of a medication is partially missing, the date will be imputed to determine whether the medication is prior or concomitant (or both).

The following rules will be applied to impute partial dates for medications:

- If start date of a medication is partially missing, impute as follows:
 - If both Month and Day are missing, then set to January 1;
 - If only Day is missing, then set to the first of the month.
- If end date of a medication is partially missing, impute as follows:
 - If both Month and Day are missing, then set to December 31;
 - If only Day is missing, then set to last day of the month.
- If start date or end date of a medication is completely missing, do not impute.

5. STUDY POPULATION

5.1. Subject Disposition

The number of patients for each of the following categories will be summarized by treatment group:

- All randomized patients;
- Patients included in the Safety population;
- Patients who completed 76-week treatment;
- Patients who completed 104-week treatment;
- Patients who discontinued early from the study and reasons for discontinuation;

Patient disposition will be summarized for all randomized patients. Summaries will include the number and percentage of patients in the mITT and Safety populations. The number and percentage of patients who prematurely discontinue study drug and the reasons for discontinuation will be summarized by treatment group.

5.2. Protocol Deviations

Protocol deviations that occurred during the randomized withdrawal study will be categorized as important or minor per the protocol deviation plan. Important protocol deviations will include, but will not be limited to, the following categories:

- Randomized patient who did not satisfy key entry criteria;
- Randomized patient who met withdrawal criteria during the study but was not withdrawn;
- Randomized patient who received the wrong treatment;
- Randomized patient who received a prohibited concomitant medication that met criteria for an important protocol deviation;
- Unintentional unblinding of treatment assignment.

Important protocol deviations will be summarized by deviation category for all patients in the mITT population. A patient listing of all important protocol deviations will be provided.

A selected subset of the major protocol deviations that are likely to affect analysis of efficacy will be identified to define the Per-Protocol population prior to the database lock. This subset will include but will not be limited to the following important protocol deviations:

- Did not satisfy key entry criteria (restricted to patients who did not meet inclusion criterion 4 of MVT-601-035, ie, patients who were not responders at the time eligibility was being assessed);
- Drug compliance during the randomized treatment period < 75%;
- Patient received prohibited concomitant medications that met criteria for important protocol deviation: restricted to patients who received prohibited concomitant medications that may cause significant drug-drug interaction;

- Unintentional unblinding of treatment assignment.

